## **III. Objectives**

**Objective 1: To determine the effect of immediate postpartum initiation of DMPA on breastfeeding.** We hypothesize that administration of DMPA immediately postpartum (i.e., before hospital discharge) will not impair breastfeeding compared to administration beginning at 12 weeks post-delivery. To increase the likelihood of detecting a negative effect if one exists, we will evaluate the primary outcome, timing of lactogenesis stage II (onset of copious milk secretion, usually occurring within 96 hours postpartum), as well as a range of secondary outcomes: breastfeeding duration, perceived need for supplementation, use of supplementation, perceived adequacy of milk production, and infant anthropometric measures, including body composition with whole-body air displacement plethysmography (OSUWMC site only). Sensitivity analysis will evaluate 1) excluding women in the open control arm and 2) determining whether the findings differ by race.

**Objective 2: To determine the effect of immediate postpartum initiation of DMPA on contraception use.** We hypothesize that putative DMPA use (i.e., blinded assignment to intervention or placebo arms) will put women on a better trajectory of contraception use by intervening during a time when they likely are highly motivated to avoid pregnancy. In contrast, women who are assigned to start DMPA after a delay risk losing motivation to initiate use. To test this hypothesis, we will compare prevalence of use of a highly-effective contraceptive method at 12 months post-delivery between women in the intervention and placebo arms versus the open control arm. Secondary outcomes will include DMPA use at 12 months. Sensitivity analyses will evaluate 1) whether the findings differ by race and 2) whether the findings differ after restricting the intervention and placebo arms to the subset of women who believe that they were in the intervention arm.

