**Table 1. Data collection by objective, location, schedule and mode of collection, and compensation.**

Objective	Data collection	Location	Schedule and mode of collection	Compensation
1,2	Enrollment Questionnaire	Participating hospital	Self-administered within 48 hrs of delivery	\$80 in cash at OSUWMC; \$80 in electronic gift card at Emory-affiliated Hospital
1	Milk Let-Down Questionnaire	Participating Hospital / text, telephone, email	Interviewer administered ≤3 times daily in person at OSUWMC or Emory-affiliated hospital, then daily via text, telephone or email during the first 7 days postpartum until lactogenesis stage II occurs	One payment of \$30 in electronic gift card at all sites
1,2	Follow-up Questionnaire	Online	Self-administered at 1, 2, 4, 6, 9 and 12 months. Questionnaires at 1, 6 and 12 months include infant anthropometric measures* from well-child visit data	\$10 per interview in electronic gift card at all sites
1	Infant adiposity (PEA POD) and other infant measures*†	OSUWMC only	Measured by trained study staff at 4 months of age	\$40 in gift card, a branded gift (e.g., a cell phone popsocket or a pen with light) worth less than \$4.00, and either parking pass or transportation by cab to appointment

OSUWMC = Ohio State University Wexner Medical Center; \*Includes weight, length, head circumference; †Visit not completed by participants who delivered at an Emory-affiliated Hospital

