## B. Study Population

We will enroll a convenience sample of 800 women. Women can enroll either prenatally or postpartum before their hospital discharge.

To enroll prenatally, women need to meet the following eligibility criteria:

- 1) Intend to deliver in the Labor and Delivery Unit at a participating ;
- 2) Are ≥18 years of age;
- 3) Speak English;
- 4) Intend to breastfeed, or express milk for their infant, for ≥6 months;
- 5) Do not want to become pregnant within the first 12 months after delivery;
- 6) Want to start use of DMPA immediately after delivery before discharge; **AND**

- 7) Intend to reside in Ohio for those who deliver at OSUWMC or intend to reside in Georgia for who deliver at an Emory-affiliated Hospital for the first 12 months after delivery.

Women will be excluded if they have any contraindications to DMPA (per package insert), which consist of the following:

- 8) Undiagnosed vaginal bleeding;
- 9) Known or suspected malignancy of breast;
- 10) Active thrombophlebitis, or current or past history of thromboembolic disorders, or cerebral vascular disease;
- 11) Liver dysfunction or disease; **OR**
- 12) Known hypersensitivity to Depo-Provera.

Women who enroll prenatally will need to rescreen following delivery to confirm their eligibility. Women enrolling after delivery or who are rescreening will need to meet criteria 2-12 above as well as the following eligibility criteria:

- 1) Are a postpartum patient in the Labor and Delivery Unit at OSUWMC or participating Emory-affiliated Hospital; **AND**
- 2) Have delivered a term, singleton infant of  $\geq 2500$  grams without any apparent health concerns.

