**Table 2. Location for recruitment, screening and enrollment by prenatal and postpartum status and type of location**

Women	Type of location	Location
Prenatal	Prenatal care at primary obstetrical facilities that refer to a participating hospital for delivery	
 
• Hospital obstetrics-gynecology outpatient clinic
 
• Faculty practices
 
• Primary One health centers
 

	Local classes for pregnant women in the community	
 
• Lactation, birthing and prenatal yoga classes
 

Finally, secondary outcomes will include infant measures collected during the follow-up questionnaire (using maternal reports of data from well-child visits) and during the 4-month visit at OSUWMC. Participants enrolled at an Emory-affiliated hospital will not complete a 4-month visit because the site lacks the ADP system. The latter will include the following: 1) percent fat mass (%FM) and fat-free mass (FFM%) measured using the validated, non-invasive whole-body air displacement plethysmography (ADP) system; 2) length with a SECA 416 digital infantometer; 3) head circumference with metric tape; 4) body weight with SECA 727 digital scale; and 5) skinfold with Holtain calipers. We will ensure consistently high-quality measurement by regular monitoring, assessing reliabilities, and refresher training.	Postpartum	Through MyChart Hospital	
 
• Tour of study hospitals during pregnancy
 
• OSUWMC and participating Emory-affiliated hospitals
 

---	------------	--------------------------	---

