Participants will be referred for DMPA at 12 weeks if in the intervention or placebo arms and at 6 weeks if in the open control arm. Participants will receive referrals for financial assistance for DMPA as appropriate. Participants will be counseled to use condoms for all sexual intercourse before receiving DMPA and will receive a supply of condoms for 12 weeks (intervention or placebo arms) or 6 weeks (open control arm). Interviewers will administer the short “Milk Let-Down Questionnaire” up to three times daily in person before discharge or until lactogenesis II occurs.

**Follow up.** If lactogenesis II does not occur before hospital discharge, participants will be asked to complete the “Milk Let-Down Questionnaire” daily via telephone, text or email for the first 7 days postpartum until the event occurs.

Participants will be instructed to complete an online “Follow-up Questionnaire” at 1, 2, 4, 6, 9 and 12 months post-delivery. The “Follow-up Questionnaire” will collect data on breastfeeding behaviors and perceptions; contraception use; and infant physical measurements from well-child visits. If the participant does not have the information from her infant’s well-child visit on-hand or if the information that she provides is incomplete or appears to be inaccurate, we will extract the data on the infant’s weight, length and head circumference from the medical records at their pediatrician’s office.

Participants enrolled at OSUWMC will be asked to return with their infant to OSUWMC for a four-month visit, during which infant measures will be collected (infant adiposity via PEA POD, weight, length, head circumference and skinfold) and recorded on the “Four-month Visit Form.” If women have not already completed their 4-month online “Follow-up Questionnaire” at the time

of the in-person visit, they will be instructed to do so using a computer established for this purpose at OSUWMC.

**Compensation.** Participants will receive compensation (amounts specified in Table 1) for their time and travel expenses. The compensation amounts are in-line with recent research with similar populations.

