## E. Statistical Considerations

**Analysis of Objective 1.** A noninferiority analysis will be used for the primary outcome of time to lactogenesis II. Noninferiority trials are appropriate when the goal is to show that a new treatment (immediate postpartum DMPA initiation) is not clinically worse than an active control (placebo injection, open control); this is in contrast to the standard superiority trial, in which the goal is to show that a new treatment is *better* than the control. Noninferiority will be determined based on the relationship of two-sided 95% confidence intervals (CIs) to pre-specified noninferiority margins. Noninferiority of the intervention arm over the other two arms combined will be accepted if the upper bound of a two-sided 95% CI for the mean difference between groups (intervention – placebo and open control) is less than 6 hours. Although a clinical significant delay in lactogenesis has not been well established, this difference is conservatively sensitive for a noninferiority test given that many common medical interventions (e.g., epidural anesthesia, labor induction, and Cesarean delivery) have been shown to delay lactogenesis stage II by up to 12 hours. Furthermore, the interval of 6 hours is consistent with previous research. Sensitivity analysis will evaluate excluding women in the open control arm (i.e., comparing the intervention arm to the placebo arm).

As a sensitivity analysis, we will repeat these analyses accounting for infant sex as a biological variable, as well as potential confounders including maternal factors that could affect lactogenesis: age, pre-pregnancy body mass index, primiparity, psychosocial stress, diabetes, hypertension, unscheduled Cesarean section, and intention at birth to exclusively. We also will evaluate whether the relationship of interest (e.g., immediate postpartum DMPA initiation and time to lactogenesis II) varies by maternal Black race. Finally, although we expect only a negligible amount of missing data for the primary outcome, we will assess the sensitivity of results to missing data by performing multiple imputation analyses under both missing at random and missing not at random assumptions.

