For secondary outcomes (breastfeeding duration, perceived adequacy of milk production, etc.), we do not have *a priori* set noninferiority margins, and thus a traditional superiority analysis will be conducted (test for significant differences using t-tests or chi-squared tests as appropriate). We will report two-sided 95% CIs for all outcomes so that post-hoc noninferiority analyses could be conducted (i.e., to evaluate whether the CI covers a specified noninferiority margin).

**Analysis of Objective 2.** A traditional superiority analysis will be used to compare rates of use of a highly effective method of contraception (defined here as DMPA, implant, IUD, sterilization, pill, patch, or ring) at 12 months post-delivery among women in the intervention or placebo arm versus those in the open control arm. An intent-to-treat analysis will be conducted using a chi-squared test to compare the percentages of women using contraception in each group (intervention + placebo versus open control). As a sensitivity analysis, we will repeat this analysis using logistic regression in order to account for potential confounders such as maternal age, parity, gravidity, socioeconomic status, sexual activity, and prior contraceptive history. We will also repeat analyses restricting those in the intervention or placebo arm to the subset of

women who believe that they received DMPA at enrollment regardless of the accuracy of their belief as an additional sensitivity analysis. Furthermore, we will evaluate whether the relationship between immediate postpartum DMPA initiation and contraception use at 12 months differs by maternal Black race.

Given that the contraception use outcome is measured at 12 months, we anticipate some missing data; however, we have no reason to believe dropout will be differential across arms. Thus, we will assess sensitivity of results to missing data using multiple imputation analyses under both missing at random and missing not at random assumptions. The secondary outcome (DMPA use at 12 months) will be analyzed with similar methods.

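### Infant growth and body composition are compared by t-test without adjustment for birth size or age at measurement, which gives up precision that is cheap to recover

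*Combined protocol and SAP*

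**What the plan says.** Section III includes among the secondary outcomes of Objective 1 "infant anthropometric measures, including body composition with whole-body air displacement plethysmography". Section V.C gives the detail: weight, length and head circumference from the follow-up questionnaires, and at the 4-month visit the same measures plus skinfold, %FM and FFM%.

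The measures have two sources. Table 1 states "Questionnaires at 1, 6 and 12 months include infant anthropometric measures", taken from well-child visits. Section V.D (Follow up) likewise has the questionnaire collect "infant physical measurements from well-child visits", with the pediatrician's records as the fallback when the mother's information is unavailable, incomplete or looks wrong. The 4-month measures are "Measured by trained study staff at 4 months of age", at OSUWMC only. Neither source has a stated age window.

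For analysis, Section V.E says that secondary outcomes have no preset noninferiority margin and get a superiority analysis: "test for significant differences using t-tests or chi-squared tests as appropriate". Two-sided 95% CIs are promised for every outcome. No covariate is named, and the plan does not say whether growth is analysed as attained size, gain or z-score.

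Two other places bear on the point. Section V.B requires "Have delivered a term, singleton infant of" at least 2500 g, so birth weight is checked before randomization. The one covariate-adjusted analysis under Objective 1 is a sensitivity analysis within the primary-outcome text, "accounting for infant sex as a biological variable" together with maternal factors. Neither birth size nor age at measurement is on that list.

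**The concern.** An infant's size depends on its size at birth, its sex and its exact age when measured. A two-group t-test leaves all of that variation in the error term, although birth weight is known at baseline.

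Precision matters here for two reasons. Section III says the range of outcomes was chosen to raise the chance of seeing a negative effect, and under a superiority test avoidable noise works against that. Section V.E also offers the CIs so that noninferiority can be judged afterwards, and the width of the interval then largely decides the answer. Precision is scarcer still for body composition, which is measured at one site.

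Section V.D describes stratified randomization without naming the strata, so the plan gives no assurance of balance on birth size.

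**Working it through.** **1. The plan's own figures.** The plan gives no SD or power for any growth outcome, so there is no growth figure to reproduce. Its primary-outcome figures do reproduce. Power = Φ(6 / [18·√(1/n₁ + 1/n₂)] − 1.96) gives 90.2% for 143 vs 286 (stated 90%), 86.8% for 128 vs 256 (stated 87%) and 80.5% for 143 vs 143 (stated 80%). None of these is disputed.

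**2. Inputs for growth.**
- Grouping: intervention against the two control arms combined, as for the primary outcome. Section V.E does not restate the grouping for secondary outcomes, so this is an assumption.
- Numbers: 143 per arm less 20% gives 114 vs 228. The 20% is stated for Objective 2 at 12 months and is applied to growth as an assumption.
- Correlation r between birth size and later size: not in the documents; assumed 0.2 to 0.6.

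**3. Unadjusted precision, in SD units.** SE = √(1/114 + 1/228) = 0.1147. The 95% half-width is 1.96 × 0.1147 = 0.225. The difference detectable with 80% power is (1.960 + 0.842) × 0.1147 = 0.321.

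**4. After adjusting for birth size.** Residual variance is multiplied by (1 − r²), so half-width and detectable difference are multiplied by √(1 − r²), and effective N by 1/(1 − r²). Chance imbalance in birth size lies within ±0.225 SD in 95% of trials. It moves the unadjusted estimate by r times that amount.

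| Assumed r | 95% half-width (SD) | Detectable at 80% power (SD) | Effective N | Power at 0.321 SD | Shift of unadjusted estimate, 95% limit (SD) |
|---|---|---|---|---|---|
| no adjustment | 0.225 | 0.321 | ×1.00 | 80% | n/a |
| 0.2 | 0.220 | 0.315 | ×1.04 | 82% | 0.045 |
| 0.4 | 0.206 | 0.295 | ×1.19 | 86% | 0.090 |
| 0.6 | 0.180 | 0.257 | ×1.56 | 94% | 0.135 |

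**5. Validity of the t-test.** In 20,000 simulated trials with no effect, 114 vs 228 and r = 0.4, the unadjusted t-test rejected in 4.9%. Among the trials in the outer 5% of birth-size imbalance (1,013 trials), it rejected in about 11.5%.

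**6. Age scatter in raw weight.** The share of total variance is (b·s)² / [(b·s)² + SD²], where b is daily gain, s the SD of age and SD the within-age SD of weight. All three are assumptions.
- s = 7 days, b = 15 g/day, SD = 750 g: 105² / (105² + 750²) = 11,025 / 573,525 = 1.9%.
- s = 7 days, b = 25 g/day, SD = 600 g: 175² / (175² + 600²) = 30,625 / 390,625 = 7.8%.
- Over the same ranges of b and SD, s = 3 days gives 0.4% to 1.5% and s = 14 days gives 7% to 25%.
- Faster early growth, b = 30 g/day with SD = 500 g and s = 7 days: 210² / (210² + 500²) = 44,100 / 294,100 = 15%.

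**The case against.** The strongest reply is that nothing is invalid. A t-test between randomized groups is unbiased, and its CI already allows for chance imbalance in birth size; the 4.9% rejection rate in step 5 bears this out. On that view, leaving covariates out for secondary outcomes that were never powered is a choice about efficiency. This stands. What remains is the width of the interval and the position of the estimate in the one trial that is run.

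The plan also fixes no scale, and a t-test on z-scores is still a t-test, so an analyst could standardise for age and sex within the stated method. That is possible, but the plan does not say it will be done, and age- and sex-standardised z-scores alone would not bring in birth size.

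The adjusted sensitivity analysis might be read as reaching the infant outcomes, since its scope is loosely worded. If so, infant sex is covered. Birth size and age at measurement are still absent from its list, and its maternal factors are chosen for their effect on lactogenesis.

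Finally, the gain rests on assumed correlations. Restricting births to term infants of at least 2500 g tends to lower r, and the gain is likely to be smaller for 12-month size and %FM than for early weight and length. This also stands, which is why the range starts at r = 0.2, where the gain is slight.

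**Conclusion.** The omission is real and the remedy is cheap. Adjusting for birth size narrows the interval by about 2% at r = 0.2 (0.225 to 0.220 SD), 8% at 0.4 (to 0.206) and 20% at 0.6 (to 0.180), equal to 4%, 19% or 56% more infants. These figures rest on the assumed r, the 20% attrition and the 1:2 grouping. For body composition the numbers are smaller and the intervals wider, because only one site measures it.

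Four stronger readings are tempting, and the documents do not support them:
- *The t-test is biased or inflates error.* It does not do so over randomization. The 11.5% rate applies only to the most imbalanced trials.
- *Imbalance in birth size passes in full into the estimate.* It passes through multiplied by r.
- *Measurement ages are known to vary widely.* The plan reports no scatter. Variation is inferred from the use of routine visits without a window at 1, 6 and 12 months. It applies less at 4 months, where study staff measure the infants.
- *Growth is a designated safety endpoint.* The plan calls these measures secondary outcomes, although their stated purpose includes detecting harm.

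**What to change.** In the secondary-outcome paragraph of Section V.E, for weight, length, head circumference, skinfold, %FM and FFM%, replace the t-test with linear regression on arm, adjusted for birth weight, infant sex and exact age at measurement. Where age- and sex-standardised z-scores exist, these may be analysed instead, adjusted for the birth-weight z-score. Report the adjusted 95% CI. Naming the covariates now also rules out choosing them after the data are seen.

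The change needs no extra participants or visits, but it may need more than SAP wording. Section V.B shows birth weight only as a threshold. Section V.D lists weight, length and head circumference for extraction from records, without a date. Confirm that the forms capture actual birth weight and the date of each measurement, and add a field for either one that is missing.

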## V. Procedures

### A. Overview

We will conduct an RCT of 429 women and their infant per arm (Figure 1). We will promote the study and enroll eligible, consenting women 1) prenatally at the primary obstetrical facilities that refer to the study sites for delivery; 2) prenatally at pregnancy-related classes in the community or 3) postpartum at a participating hospital after their delivery and before their discharge. We will enroll approximately 800 women because we anticipate a high number of screening failures before randomization. Our power is based on having approximately 143 women-infant pairs randomized to each of the three arms.

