**Sample size.** Sample size was based on providing high (90%) power for the primary outcome of Objective 1 (time to lactogenesis II), while also ensuring appropriate power for Objective 2. We assumed that all groups would have a mean of 65 hours with a common standard deviation of 18 hours, based on a previous study, which was consistent with past research. Setting the noninferiority margin at 6 additional hours, **with a type 1 error rate of 0.05 (two-sided 95% CI), we require 143 women randomized to each group to achieve 90% power.** As this outcome is measured very soon after randomization, we expect to have it measured on all randomized women. However, we note that even if we have a small amount of missing data for this outcome, we will still have high power. For example, if we have 10% missing data (i.e., time to lactogenesis II measured on 128 women per group), we will still have 87% power. Additionally, this sample size ensures adequate power for our sensitivity analysis comparing intervention to placebo (i.e., excluding women in the open control arm); we will have 80% power for the noninferiority analysis comparing these two groups (under the same assumptions as stated above).

The sample size justified for Objective 1 also will provide high power for Objective 2, which will be assessed using traditional superiority analyses. Based on a recent analysis of data from the National Survey of Family Growth, we assume that the rate of highly effective contraceptive use will be 50% in the open control arm. We conservatively assume a 20% attrition rate at 12 months, thus will have n=114 women in the open control arm and n=228 women in the combined injection arms (DMPA; placebo). With this sample size of randomized women, we will have 81% power to detect a contraceptive use rate of 66% in the intervention/placebo group, corresponding to a relative risk of RR=1.32.

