## **VIII. Internal Validity**

A primary limitation of the trial involves potential issues of generalizability. For example, we are restricting the study to exclude infants who are preterm, low birthweight, or have apparent health complications. Consequently, our findings cannot be extended to infant subgroups arguably most in need of the intervention. Although breastfeeding could be especially important for these subgroups, their inclusion could hinder our ability to detect differences attributable to DMPA exposure. A future study would focus on these special groups. Another potential issue is the linkage, albeit controversial, between DMPA and increased risk of HIV acquisition found in non-randomized trials. However, even if the ongoing RCT eventually supports a causal relationship, DMPA is a popular method that can be expected to continue to have an important role in the contraception method mix.

The trial will not answer other research questions that may be of interest. For example, we will not evaluate whether early administration of DMPA affects milk composition. Prior assessments have been unable to interpret the clinical significance of any difference detected in milk composition. For this reason, we are focusing on outcomes with clearer clinical significance. While other breastfeeding outcomes are important to maternal and infant health, we selected the primary outcome, timing of lactogenesis stage II, because it is closely tied to the possible mechanism by which DMPA exposure could impair lactation. Furthermore, this outcome is less susceptible to bias than other possible breastfeeding outcomes. For example, breastfeeding duration could be biased if even a minor proportion of participant attrition occurs during follow up and if this attrition were differential by study arm.

We could experience logistical challenges while fielding the trial. We plan to randomize women within 48 hours of delivery. However, to reflect real-life, clinical circumstances, we will randomize women within 96 hours of delivery, if needed. In this case, we would conduct sensitivity analyses to determine whether the timing of the initial DMPA injection affects the primary outcomes.

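### The main Objective 2 test is called intent-to-treat but in effect analyses only women with a month-12 answer, and leaves the earlier contraceptive reports unused

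*Combined protocol and SAP*

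**What the plan says.** Section V.E (Analysis of Objective 2) compares use of a highly effective method "at 12 months post-delivery among women in the intervention or placebo arm versus those in the open control arm". The test is described in one sentence: "An intent-to-treat analysis will be conducted using a chi-squared test to compare the percentages of women using contraception in each group". Nothing there says how a randomised woman with no month-12 answer is counted.

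The same section expects some missing month-12 data, states that "we have no reason to believe dropout will be differential across arms", and commits to multiple imputation under both MAR and MNAR as a sensitivity analysis. It names no imputation model, predictors or MNAR shifts.

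On numbers, section V.A says: "Our power is based on having approximately 143 women-infant pairs randomized to each of the three arms". The sample-size paragraph of V.E then says: "We conservatively assume a 20% attrition rate at 12 months, thus will have n=114 women in the open control arm and n=228 women". The larger figure is for the DMPA and placebo arms taken together. The paragraph quotes 81% power for 66% against 50% use.

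Three other places bear on the point:
- Contraceptive use is asked in the online questionnaires at months 1, 2, 4, 6, 9 and 12 (V.D, Follow up).
- Eligibility requires that each woman "Want to start use of DMPA immediately after delivery before discharge" (V.B), and the open control arm is unblinded (V.A).
- Section VIII, explaining the choice of the Objective 1 outcome, notes that "breastfeeding duration could be biased if even a minor proportion of participant attrition occurs during follow up and if this attrition were differential" by arm.

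**The concern.** An intent-to-treat label implies that all randomised women count in the comparison. A chi-squared test on month-12 answers can count only those who gave one, unless a rule assigns values to the rest. The plan has no such rule, and its power figure matches the analysis without those women.

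An observed-case comparison of percentages is sound if, within each group, answering is unrelated to use. It also has the right error rate under the null if the relation is the same in both groups. Equal dropout totals are neither necessary nor sufficient. The plan's reassurance concerns whether dropout differs across arms, which is not quite the condition that matters.

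The comparison sets an arm that knows it received no injection against two blinded arms, in women who all wanted an injection before discharge. A different link between use and response in the two groups is therefore plausible. If it exists, the Objective 2 result is biased in a direction nobody can state in advance. Five rounds of earlier reports could correct part of that bias, but the main test does not use them.

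**Working it through.** **Inputs from the documents.** 143 per arm (V.A); 20% attrition, 114 and 228 analysed, 50% and 66% use, 81% power (V.E). Two-sided 0.05 is stated for Objective 1 and assumed here for Objective 2. All retention-by-use rates and month-to-month agreement rates below are assumptions, because the documents give none.

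**1. The plan's own figure.** 143 × 0.8 = 114.4 and 286 × 0.8 = 228.8, truncated to 114 and 228. The total is 342, and 429 − 342 = 87 (20.3%).

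Power = Φ[(|d| − 1.96·s0)/s1], with s0 the pooled and s1 the unpooled standard error. Here d = 0.16 and the pooled rate is (57 + 150.48)/342 = 0.607. So s0 = √(0.607 × 0.393 × (1/114 + 1/228)) = 0.0560 and s1 = √(0.25/114 + 0.2244/228) = 0.0564. Then (0.16 − 0.1098)/0.0564 = 0.89, and power is 81.3%. The stated 81% reproduces on 342 women. With all 429 outcomes observed (143 and 286), it would be 89.1%.

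**2. How far missing outcomes could move the result.** Take 57/114 and about 150/228 users among responders, with 29 and 58 women missing.
- Control: 57/143 = 39.9% to 86/143 = 60.1%.
- Injection: 150/286 = 52.4% to 208/286 = 72.7%.
- Difference: 52.4 − 60.1 = about −8 points, to 72.7 − 39.9 = about +33 points.

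These are extreme bounds, not forecasts.

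**3. Bias with equal totals.** If true use is p, and users and non-users are retained at rates u and v, observed use is pu/[pu + (1 − p)v]. With p = 0.50, u = 0.90 and v = 0.70, total retention is 80% and observed use is 0.45/0.80 = 56.25%. With 80% of both retained, it is 50%.

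| Assumed pattern | True use (control / injection) | Observed difference | Rejection rate |
|---|---|---|---|
| 90/70 in one group, 80/80 in the other | 50 / 50 | 6.25 points | about 19% |
| 90/70 in both groups | 50 / 50 | 0 | 5.0% |
| 85/75 in control, 80/80 in injection | 50 / 50 | 3.1 points | about 8.5% |
| 90/70 in control, 80/80 in injection | 50 / 66 | 9.75 points | about 42% |
| 90/70 in both groups | 50 / 66 | 15.1 points | about 80% |

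For the first row (pattern in control): s0 = 0.0573 and s1 = 0.0571. The main tail is Φ[(0.0625 − 0.1123)/0.0571] = Φ(−0.87) = 0.19, and the other tail is about 0.001.

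**4. What the interim reports can recover.** Suppose that month-9 use is known for everyone, is 50%, and agrees with month-12 use in 80% or 85% of women.
- Retention of 90/70 by *month-9* use (MAR given that report): observed month-12 use is (0.45 × 0.80 + 0.35 × 0.20)/0.80 = 53.75% at 80% agreement, and 54.4% at 85%. The bias is 3.75 to 4.4 points. Conditioning on month-9 use removes all of it.
- Retention of 90/70 by *month-12* use itself (MNAR): within month-9 users, observed use is 0.72/0.86 = 83.7%; within non-users it is 0.18/0.74 = 24.3%. Their average is 54.0%, so 4.0 of the 6.25 points remain. At 85% agreement 3.2 remain. MAR adjustment removes about a third to a half.

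**The case against.** The plan does not overlook missing data. It anticipates them, allows for them in the power calculation, and commits to imputation under two mechanisms. A chi-squared test on available outcomes by assigned arm, with imputation as a sensitivity analysis, is a recognised order of analyses, and it implies that the chi-squared result governs. All of this stands. A reader might infer that the plan rests only on its statement about dropout, but the commitment to MAR and MNAR imputation rules that out.

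A reader might also infer that the documents show dropout will differ by arm. They do not. Section VIII is conditional and concerns another outcome. Objective 2's remark about lost motivation concerns starting DMPA, not answering questionnaires. Open-control women are referred for DMPA at 6 weeks, and sections V.D and VIII describe substantial retention efforts. If women who lapse from use also stop answering, that could happen equally in every arm, and the second and fifth rows of the table show that little harm then follows.

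The 19% and 42% figures come from a one-sided assumed pattern that depends on month-12 use itself. MAR imputation does not fully correct that pattern, so these figures cannot be offered as the gain from the change.

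The objection leaves the core standing. The main test has no missing-outcome rule, its label claims more than it delivers, and it sets aside relevant data already collected.

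**Conclusion.** The point holds as a cheap improvement to the Objective 2 analysis. It does not invalidate the trial, whose primary outcome (time to lactogenesis II) is measured within days of delivery.

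That the main test is an observed-case analysis is an inference from the missing rule and from the power on 342 women; the documents do not use the term. The 87 missing women are a planning figure that the protocol calls conservative, not a known loss.

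Under the assumptions shown, the null bias ranges from zero (same link in both groups) through 3.1 points (type I error about 8.5%) to 6.25 points (about 19%). Neither its presence nor its direction can be derived from the documents. Using the interim reports would remove bias from dropout that they explain, but only part of any bias from dropout that depends on month-12 use itself. MNAR analyses therefore stay necessary.

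**What to change.** In section V.E (Analysis of Objective 2):
- Make the main analysis cover all randomised women, by multiple imputation of month-12 use under MAR. Impute separately by arm, with baseline covariates, site and the contraceptive reports at months 1, 2, 4, 6 and 9 as predictors.
- Keep the observed-case chi-squared test as a sensitivity analysis.
- Keep the MNAR analyses as sensitivity analyses, with arm-specific shifts fixed in advance.
- State that the MAR imputation result governs, and report attrition by arm.

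The change needs no new data, visits or participants. Its cost is the work of specifying the imputation model and the MNAR shifts, which the plan now leaves open and which the sensitivity analyses already promised would need in any case.
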